- Listening effort and fatigue (Effort Assessment Scale, EAS; Fatigue Assessment Scale; FAS; Listening Effort Questionnaire-Cochlear Implant, **LEQ-CI***) at 1, 3, 6, and 9 months post first treatment activation
- Tinnitus severity (Tinnitus Functional Index, TFI) at 1, 3, 6, and 9 months post first treatment activation
- Tinnitus loudness (Visual Analogue Scale of Loudness, VAS-L) immediately before and after first treatment activation and at 1, 3, 6, and 9 months post first treatment activation
- Mood (Hospital Anxiety and Depression Scale, HADS) at 1, 3, 6, and 9 months post first treatment activation
- Hearing-specific quality of life (Nijmegen Cochlear Implant Questionnaire, NCIQ; York Binaural Hearing-Related Quality of Life, YBHRQL; Hearing Handicap Inventory for Adults, HHIA) at 1, 3, 6, and 9 months post first treatment activation
- Health-related Quality of Life (EuroQol EQ-5D-5L; Health Utilities Index Mark 3, HUI3; ICEpop CAPability measure for Adults, ICECAP-A) at 1, 3, 6, and 9 months post first treatment activation
- Global ratings of change in hearing and quality of life at 1, 3, 6, and 9 months post first treatment activation: At each follow up appointment following first treatment activation, participants will be asked to indicate on 7-point Likert scale ranging from 'Much Worse' to 'Much Improved' whether hearing and quality of life have improved or worsened relative to two anchor points: (1) immediately prior to first treatment activation; and (2) since the last trial appointment.
- Device usage (participant self-report) at 1, 2, 3, 4, 5, 6, 7, 8 and 9 months

*Data to be collected using LEQ-CI questionnaire once licence is in place

Safety outcomes

From randomisation to 9 months post first treatment activation, safety data, including number of expected AEs and SAEs and unexpected related SAEs will be summarised with descriptive statistics according to the treatment the participant received, irrespective of randomisation. Where a participant did not receive their allocated treatment but had an expected AE, or SAE this will be indicated.

Stopping rules and discontinuation

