Following the baseline visit, participants in the intervention arm will attend a meeting of the multi-disciplinary clinical team at which surgical consent will be obtained by a participating CI surgeon to whom that responsibility has been delegated, and at which the MDT will confirm the choice of ear to be implanted based on clinical judgement. All participants will be offered a danalogic GN HA for the ear that will not be implanted. If taken up, the HA will be fitted in line with standard practice at site for a contralateral HA and no later than 6 months following CI activation. All participants will be encouraged to continue to use their HAs in the period before surgery, and in their non-implanted ear following surgery.

It is our expectation that Cochlear implantation surgery occurs within 3 months following randomisation. Unilateral cochlear implantation will be provided in accordance with the quality standards of the British Cochlear Implant Group (BCIG 2018, or latest available version). Participants will attend for surgery on the designated date. This surgery is routinely undertaken on a day case basis in many hospitals, but the participant will be advised as to whether an overnight stay of 1 or more nights will be required or is anticipated.

The choice of CI system will be restricted to the trial devices, which are those manufactured by Cochlear™ Ltd and the most appropriate device for patients with significant residual hearing in the implanted ear. Sites will need to specify the trial devices that each participating surgeon routinely implants. Routine is defined as at least 5 implantations performed per year. NCTU will keep a log of which sites are implanting which devices. Any changes to the pre-specified choice of device will need to be discussed with the NCTU. A surgical protocol will be defined prior to start of recruitment in consultation with CI surgeons, such as those involved in the trial setup, and departures from the protocol will be permitted only where clinically necessary and will be captured via the trial documentation.

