Listening effort and fatigue	FAS total score, EAS total score, LEQ-CI* total score at 1, 3, 6, and 9 months. Scores will be calculated using the algorithms in the questionnaire manuals.
Tinnitus severity	Global 25-item TFI score Global 19-item TFI score (excluding sleep and auditory subscales) TFI scores for 8 subscales All at 1, 3, 6, and 9 months.
Tinnitus loudness	
 • VAS-L rating. Participants mark the loudness of their tinnitus at any point along the numerical scale, with word descriptors utilised as anchor points at 0 for “extremely weak,” 30 for “moderate,” 50 for “strong,” 70 for “very strong,” and 100 for “extremely strong” tinnitus loudness. 
Immediately before and after first treatment activation, and at 1, 3, 6, and 9 months.

Mood	HADS anxiety and depression subscale scores at 1, 3, 6, and 9 months.
Hearing-specific quality of life	NCIQ total and six subdomain scores YBHRQL binaural utility value HHIA total score and two subscale (emotional and social/situational) scores All at 1 month, 3 months, 6 months, and 9 months.
Health-related quality of life	HUI3 multi-attribute utility value, EQ-5D-5L health utility value using EQ-5D-3L UK value set ICECAP-A tariff value All at 1 month, 3 months, 6 months, and 9 months.
Global ratings of change	Likert scale ratings of change (7 points from much worse to much improved) in hearing and quality of life relative to two anchor points (immediately prior to first treatment activation; since the last trial appointment) at 1, 3, 6, and 9 months.
Audiometric thresholds	Unaided audiometric thresholds at first treatment activation and at 3, 6 and 9 months.

Outcome Measure	Derivation
	Aided audiometric thresholds at first treatment activation and at 3 and 9 months.

*Data only to be collected using LEQ-CI questionnaire once licence is in place

Assessment of safety

Safety data, including number of expected AEs and SAEs and unexpected related SAEs will be summarised with descriptive statistics according to the treatment the participant received, irrespective of randomisation; where anyone received more than one treatment (e.g., HA then CI) these will be summarised separately. Where a participant did not receive their allocated treatment but had an expected AE, or SAE this will be indicated.

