The number of participants experiencing at least one AE or SAE will be summarised using descriptive statistics. The total number and type of AEs and SAEs will also be summarised, overall and by event.

Procedures for missing, unused and spurious data

It is planned that several strategies to investigate the effect of missing primary outcome data will be undertaken as sensitivity analyses, including the use of multiple imputation with chained equations and minimisation variables as covariates. More information on methods will be included within the SAP.

Definition of populations analysed

Full analysis set, including safety: All randomised participants for whom at least one post-baseline assessment is available.

There will not be a per-protocol dataset.

ADVERSE EVENTS

Reporting requirements

The collection and reporting of Adverse Events (AEs) will be in accordance with the UK Policy Framework for Health and Social Care Research 2017 and the requirements of the Research Ethics Committee (REC). Definitions of different types of AEs are listed in the table of abbreviations and definitions.

Reporting Period

Trial related AEs will be collected from time of randomisation (baseline visit) until the collection of the primary outcome (9 months post-treatment onset).

Definitions

Adverse Events

An **adverse event** is any unfavourable and unintended sign, symptom, syndrome or illness that develops or worsens during the period of observation in the trial.

An AE does include a / an:

1. exacerbation of a pre-existing illness.
2. increase in frequency or intensity of a pre-existing episodic event or condition.
3. condition detected or diagnosed after medicinal product/device administration even though it may have been present prior to the start of the trial.
4. continuous persistent disease or symptoms present at baseline that worsen following the start of the trial.

An AE does not include a / an:

1. medical or surgical procedure (e.g., surgery, endoscopy, tooth extraction, transfusion); but the condition that led to the procedure is an AE.
2. pre-existing disease or conditions present or detected at the start of the trial that did not worsen.
3. situations where an untoward medical occurrence has not occurred (e.g., hospitalisations for cosmetic elective surgery, social and / or convenience admissions).

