4. disease or disorder being studied, or sign or symptom associated with the disease or disorder unless more severe than expected for the participant's condition.
5. overdose of concurrent medication without any signs or symptoms.
6. expected AE as listed below.

Expected adverse events

The treatments provided to both intervention arms are widely available within the NHS, used in standard care and considered to be safe. Known adverse events (listed in the table below) are related to their respective trial interventions. These events are secondary outcomes and will be collected as part of the eCRF. The number of occurrences of expected AEs and SAEs will be regularly reviewed throughout the trial by the TMG and the DMC.

Expected AE	Expected SAE
Related to Cochlear Implantation (intervention arm only)	
Facial nerve stimulation (temporary)	Facial nerve stimulation (chronic)
Patient reported decreased hearing ability or loss of residual acoustic hearing (temporary or permanent)	The inability to use the implant or a hearing aid in that ear
Vestibular dysfunction (temporary)	Vestibular dysfunction (chronic)
Perception of non-auditory sensations (temporary or permanent)	Infection requiring hospitalisation (e.g., meningitis and the need for vaccination)
New onset or exacerbation of pre-existing tinnitus	Any surgical complication that requires hospitalisation
Altered taste	Need for revision surgery, reimplantation or explantation
Facial weakness	Subdural injury
Acute otitis media or any other infection treated by oral antibiotics	Chronic pain in or around the implant site or hearing aid
Perilymph fistula	

Expected AE	Expected SAE
Concurrent cerebrospinal fluid (CSF) leakage	
Subcutaneous haematoma	
Unsatisfactory device insertion (e.g., misplacement of electrode array, incomplete electrode insertion, tip fold-over)	
Failure of component parts	
Related to Hearing Aids (intervention and comparator arms)	
Ear infection	None
Exacerbation of eczema	

Serious Adverse Events

A Serious Adverse Event (SAE) is any adverse event occurring following trial mandated procedures that results in any of the following outcomes:

1. Death
2. A life-threatening adverse event
3. Inpatient hospitalisation or prolongation of existing hospitalisation
4. A disability / incapacity
5. A congenital anomaly in the offspring of a participant

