A distinction is drawn between serious and severe AEs. Severity is a measure of intensity whereas seriousness is defined using the criteria above. Hence, a severe AE need not necessarily be serious.

Important medical events that may not result in death, be life-threatening, or require hospitalisation may be considered a SAE when, based upon appropriate medical judgment, they may jeopardize the patient or participant and may require medical or surgical intervention to prevent one of the outcomes listed in this definition.

Events deemed by the investigator to be related to COVID-19 infection will not be reportable.

If an adverse event, *not listed as expected AEs above*, meets, or potentially meets, the SAE criteria it will be assessed for seriousness, and causality.

Causality

Not related or improbable: a clinical event including laboratory test abnormality with temporal relationship to trial device which makes a causal relationship incompatible or for which other treatment, drugs, chemicals or disease provide a plausible explanation. This will be counted as “unrelated” for notification purposes.

Possible: a clinical event, including laboratory test abnormality, with temporal relationship to trial device which makes a causal relationship a reasonable possibility, but which could also be explained by other treatments, devices, drugs, chemicals or concurrent disease. This will be counted as “related” for notification purposes.

Probable: a clinical event, including laboratory test abnormality, with temporal relationship to trial device which makes a causal relationship a reasonable possibility, and is unlikely to be due to other treatments, devices, drugs, chemicals or concurrent disease. This will be counted as “related” for notification purposes.

Definite: a clinical event, including laboratory test abnormality, with temporal relationship to trial device which makes a causal relationship a reasonable possibility, and which can definitely not be attributed to other causes. This will be counted as “related” for notification purposes.

Recording and Reporting of Adverse Events

The below section **does not pertain to** expected AEs and SAEs (included in table of expected events above) which do not require expedited reporting with a trial SAE form. These events are secondary outcomes recorded in medical notes and collected as part of the eCRF, that will be routinely centrally monitored and reported.

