All adverse events (AEs) will be recorded as they are reported whether spontaneously volunteered or in response to questioning about wellbeing at trial visits. The questioning about AEs will cover the current visit as well as the period of time between the previous and the current visit. A note of any concomitant medication will also be made, where available, so that a full assessment of the AE can be made.

Abnormal test results that are deemed clinically significant by the investigator and that lead to a change or temporary or permanent discontinuation in the use of the device or require intervention or diagnostic evaluation to assess the risk to the subject will be recorded as adverse events and instigate further investigation and follow up as appropriate.

All AEs and SAEs will be documented in the subject’s medical records. As both trial interventions are well established and have extensive safety profiles already available, only related, or suspected to be related, SAEs will be documented on the eCRF.

For related, or suspected to be related, events, participants should be followed up until resolution or stabilisation of the event. Follow-up information should ideally be provided on a new SAE form.

Participants will be asked to contact the trial site immediately in the event of any SAEs. The Chief Investigator or nominated deputy shall be informed immediately of any related, or suspected to be related, serious events and shall determine seriousness and relationship in conjunction with any treating medical practitioners.

SAEs will be recorded and reported to the REC and Sponsor as part of the annual progress reports.

SAEs will be reported within the statutory timeframes to the REC as stated below. The Chief Investigator will be responsible for all adverse event reporting.

The NCTU will also notify the trial funder by email from the Chief Investigator to [name] [name], Global Head of Clinical Affairs, Cochlear™ Ltd, [contact] and [name], Clinical Portfolio Manager, Cochlear™ Ltd, [contact] of any serious adverse events at the time of regulatory reporting.

The funder will notify the University by email to [contact] (cc to [contact]) of any reportable events involving devices (Cochlear™ or GN Hearing UK) at the time of reporting to the MHRA, or any other relevant regulatory authorities of any new information which becomes available to them as device manufacturers which could affect the safety of trial participants.

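### Safety is grouped by treatment received but counted from randomisation, so non-specific listed events that begin before surgery can be counted under the implant

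*Protocol*

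**What the plan says.** Five places in the protocol bear on this.

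- **Window.** Under Safety outcomes in the trial design chapter: "From randomisation to 9 months post first treatment activation, safety data, including number of expected AEs and SAEs" are summarised by treatment received. The Reporting Period section has the same start: "Trial related AEs will be collected from time of randomisation (baseline visit) until the collection of the primary outcome".
- **Grouping.** Assessment of safety, in the statistics chapter, has the data "summarised with descriptive statistics according to the treatment the participant received, irrespective of randomisation". It then adds: "where anyone received more than one treatment (e.g., HA then CI) these will be summarised separately".
- **Relatedness.** Expected adverse events states: "Known adverse events (listed in the table below) are related to their respective trial interventions". The table that follows has a long implant list, marked for the intervention arm only, and a short hearing aid list (ear infection and worsening eczema).
- **Causality.** The Serious Adverse Events section says that an event not on the list which "meets, or potentially meets, the SAE criteria it will be assessed for seriousness, and causality". The Recording and Reporting section then states that it does not apply to listed events, which go to the eCRF as secondary outcomes.
- **Timing.** Under Intervention group: "It is our expectation that Cochlear implantation surgery occurs within 3 months following randomisation". The participant duration paragraph gives 3 months from randomisation to T0 and 9 months after it. In Appendix 1 the first scheduled adverse-effect entry is at T0, which for implant recipients is activation and so follows surgery.

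**The concern.** Grouping by treatment received is a reasonable choice for safety, provided events are counted from the time that treatment began. Here the grouping looks forward to the operation while the count starts before it. A person who later receives an implant is an implant recipient for the whole window, including the weeks when nothing had been implanted.

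A causality review would normally catch such events, but for listed events relatedness is settled in advance. The protocol itself describes hearing loss in this population as often progressive and allows that it may worsen after randomisation. Tinnitus is common enough to be a minimisation factor. Events of this kind during the wait are therefore plausible.

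The safety summary answers secondary objective (c), for an irreversible operation in a group not currently offered it. A row for tinnitus or hearing decline that mixes events before and after surgery does not tell the reader what the implant did. The hearing aid list has no matching rows, so it supplies no background count to set beside them. Participants with at least one event are also to be counted, so a single infection before surgery could make someone a complication case.

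**Working it through.** **1. Tracing one event through the text.** Take a participant allocated to an implant who has an infection treated with oral antibiotics one month after randomisation, surgery at two months and activation at three.

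- Inside the window? Yes, it opens at randomisation.
- On the implant list? Yes, the row covers acute otitis media or any other infection treated that way.
- Causality assessed? No, that step is for unlisted events.
- Which group? Implant, because that is the treatment received.
- Any rule on onset relative to surgery? None in the safety outcome, statistics or adverse event sections.

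So the wording admits the event under the implant.

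**2. Which rows are exposed.** Tinnitus (new or worse), reported hearing decline, temporary vestibular dysfunction and infection given oral antibiotics can occur without surgery. Perilymph fistula, CSF leakage, unsatisfactory insertion, facial nerve stimulation, component failure and revision surgery need, or strongly imply, an operation or a device. They are not affected.

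**3. Share of the window.** The protocol's timeline adds up: 6 months of eligibility + 3 months to T0 + 9 months of follow-up = 18 months, the stated participant duration. With surgery at month s and activation at month a after randomisation, the pre-operative share is s / (a + 9).

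- Bound: s is expected to be at most 3 and a is at least s, so the share is at most 3 / (3 + 9) = 25%.
- Surgery at 2 months, activation at 3: 2 / 12 = 17%.
- Hearing aid arm, for comparison: fitting or optimisation is due within 4 months, so the pre-T0 share can reach 4 / (4 + 9) = 31%.

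The 25% treats the whole time to activation as pre-operative. Part of that time actually follows surgery, so the true share is somewhat lower. The 3 months to surgery is an expectation and not a limit, so a longer wait would raise it.

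**4. Number of events.** The protocol gives no background rate, so this is illustration only. The planned arm size is 65 (55 / 0.85 = 64.7, rounded up). A 3-month wait gives 65 × 3/12 = 16.25 person-years, and the 9 months after T0 give 65 × 9/12 = 48.75. Assume 0.1 to 0.5 non-specific listed events per person-year:

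| Assumed rate | Before T0 | 9 months after T0 |
|---|---|---|
| 0.1 | 1.6 | 4.9 |
| 0.5 | 8.1 | 24.4 |

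At any constant rate, one quarter of the background events would fall before T0. The absolute number depends wholly on the assumed rate.

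**The case against.** Several parts of the text might close the gap.

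- **The clause on more than one treatment.** Its example is a hearing aid followed by an implant, and participants in the implant arm are encouraged to wear their aids while waiting. If the clause covered the wait, however, it would class the whole implant arm as having had more than one treatment. It reads more naturally as a rule for people who change treatment, and it does not date events.
- **The restriction to trial-related events in the Reporting Period section.** This does not help for listed events, because they are declared related. One can read that declaration as only defining what is expected for reporting purposes, but no other step then decides relatedness for them.
- **The SAE definition**, which requires a trial-mandated procedure first. It does not reach the non-serious rows, and those are the exposed ones.
- **The SAP**, which is not at hand and may set an onset rule. That is possible, but the window, the grouping and the relatedness of listed events are fixed in the protocol, and the safety text does not defer them.

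Some of the opposing case stands. The instruction that "The questioning about AEs will cover the current visit as well as the period of time between the previous and the current visit" might suggest that sites must collect listed events from the whole wait. It sits in the section that excludes listed events, so it cannot carry that weight. The eCRF is not shown and may already hold onset dates. The safety analysis is descriptive, with no test or formal stopping rule attached, and events are also reported by type, so surgical and device harms stay visible in their own rows.

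**Conclusion.** The point holds in a limited form. The protocol combines a count from randomisation, grouping by treatment received and relatedness declared in advance, and has no rule on onset. Non-specific listed events that begin before surgery can therefore be counted under the implant. The exposed part of the window is at most about 25%, and this rests on surgery taking place within the expected 3 months.

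A reader might infer that pre-operative events will be counted as implant harms and that the reported complication count is therefore too high by a known amount. The documents do not support that. No passage directs that such events be counted under the implant, only a few rows are open to it, and no background rate is given. Nor do they show that the table could not be put right later, since onset dates may be on the eCRF. What is established is a stated rule that can mislead in a few rows. It is worth correcting because safety is a named objective and the correction is cheap.

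**What to change.** In the as-received summary, count implant-related events only if their onset is on or after the day of surgery. Show events from randomisation to that day in a separate pre-treatment row.

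In the hearing aid arm, show events before T0 separately as well, and do not drop them. Participants already wear hearing aids at entry, so an aid-related event before the trial fitting or optimisation is still informative. People who change treatment stay under the existing clause.

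Use the onset date of each listed event, and add it to the eCRF if it is not already there. State the rule in Assessment of safety, and align the Safety outcomes, Reporting Period and Expected adverse events sections with it.

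Cost: a sentence or two of text, one date field at most and one extra table row. No new visits are needed.

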Following the implant surgery, a date for initial implant activation will be arranged, which defines first treatment activation for participants in the intervention arm. Initial implant activation will be conducted by a qualified audiologist and involves fitting the sound processor component of the implant system and switching on the implant for the first time. Recipients will all be issued with the latest model(s) of sound processor provided routinely by the participating sites at the time of their first treatment activation and will have access to device accessories. The number and choice of accessories offered to trial participants will follow current routine practice across the participating sites.

Participants will then be scheduled to attend the trial site on multiple occasions throughout the 9 months following initial activation for follow up visits. The research visits for the intervention group may coincide with routine care appointments, as per the standard care at each CI site (e.g., fitting appointments with audiologists and auditory rehabilitation and communication training). The timing of these visits will be based on the routine post-cochlear implantation care pathway for adults at each trial site. Trial research visits at which outcomes will be assessed have been designed to align with these fitting appointments, all of which are conducted by qualified audiologists. Trial sites may choose for some or part of the post-operative care pathway to be carried out remotely using telehealth systems to reflect routine practice at that time.

Comparator group

Those randomised to the HA group will be offered bilateral danalogic GN acoustic HAs. While the HAs of all participants will have been confirmed as being appropriate for their hearing loss as part of the eligibility assessment, devices available on the NHS may not reflect the very latest available HA technology. Therefore, as with the CI group, patients in the HA group will have access to the most recent HA technology from GN Hearing UK.

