In light of the Covid-19 pandemic, the design of the trial has been reviewed to mitigate the impact of Covid-19 and to ensure that Covid-safe measures are implemented as much as possible. Previous engagement with clinical services highlighted the extent to which they have rapidly adapted routine care in response to the pandemic, including the use of remote visits where appropriate and feasible. Any visit which is conducted remotely as part of standard care can be conducted as such as part of the trial, provided it does not interfere with the delivery of the trial interventions or outcome assessments. The implementation of social distancing in the clinic (e.g., waiting in separate room during appointments), considerations for travel expenses for patients who do not wish to take public transport, and patient-facing documents will be developed with PPI input and collaboratively with trial sites to describe Covid-safe measures put into place for the participants.

STATISTICS

Methods

The data will be analysed by the trial statistician using Stata version 17.

The analysis and presentation of the trial results will be in accordance with the CONSORT guidelines. The primary approach to the primary comparative analysis will be to analyse as randomised without imputation of missing data with due emphasis being placed on the confidence intervals for the between arm comparisons. A full Statistical Analysis Plan (SAP) will be finalised prior to database lock and release of treatment allocation codes. The statistician analysing the data will remain blinded to treatment allocation until after database lock.

Continuous variables will be summarised, dependent on distribution, in terms of the mean, standard deviation, median, lower, and upper quartiles, minimum, maximum, and number of observations. Categorical variables will be summarised in terms of frequency counts and percentages.

Baseline characteristics of randomised participants will be compared between the two trial arms, using appropriate descriptive statistics; no formal statistical comparisons will be made.

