Appendix 1: Schedule of Assessments

Measure	Consent	Baseline	Treatment activation (T0) ^c	Time post T0					2,4,5,7,8 months
				1 month	3 months	6 months	9 months		
Primary outcome									
Phoneme perception measured by blinded independent assessors (AB word test @ 60 dBA)		X					X		
Secondary clinical outcomes									
Phoneme perception assessed live by an audiologist (AB word test @ 60 dBA)		X			X	X	X		
Word perception (AB word test @ 60 dBA)		X			X	X	X		
Phoneme perception (AB word test @ 70 dBA)	X						X		
Word perception (AB word test @ 70 dBA)	X						X		
Sentence perception in quiet & noise (BKB sentence test @ 70 dBA)		X			X	X	X		
Device usage (device logging)		X			X	X	X		
Audiometric thresholds (Aided, Unaided)		X	X		X	X	X		
Secondary patient-reported outcomes									
Listening difficulty (SSQ12)		X		X	X	X	X		
Listening effort & fatigue (FAS, EAS, LEQ-CI)		^a X		^a X	^a X	^a X	^a X		
Tinnitus severity (TFI)		X		X	X	X	X		
Tinnitus loudness (VAS-L)		X	^b X	X	X	X	X		
Mood (HADS)		X		X	X	X	X		
Hearing-specific QoL (NCIQ, YBHRQL, HHIA)		X		X	X	X	X		
Health-related QoL (HUI3, EQ5D, ICECAP-A)		X		X	X	X	X		
Global ratings of change				X	X	X	X		
Device usage (self-report)				X	X	X	X	X	
Safety outcomes									
Adverse effects			X	X	X	X	X		
Other assessments									
Cognitive health (HI-MoCA)		X							

^aData for the LEQ-CI to be collected using the LEQ-CI questionnaire once licence is in place. ^bThe VAS-L will be done twice at this timepoint, once immediately before treatment activation and a second time after treatment activation. ^c T0 for HA arm – Either recorded date of HA fitting/optimisation appointment or recorded date of decision that the participant will not attend or 4 months post-randomisation date (whichever occurs first). T0 for CI arm – Either the date of CI activation or the date a decision was made that surgery would not take place.

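### The safety set requires a post-baseline assessment, so a CI participant lost after surgery and before any assessment drops out of the final safety tables

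*Protocol*

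**What the plan says.** Under Statistics, Definition of populations analysed, the protocol gives a single population: "Full analysis set, including safety: All randomised participants for whom at least one post-baseline assessment is available". It adds that there will be no per-protocol dataset. It does not define a post-baseline assessment.

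Other sections bear on who should be counted for safety:

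- **Trial Design, Safety outcomes**, on the period covered by the summary: "From randomisation to 9 months post first treatment activation, safety data, including number of expected AEs and SAEs and unexpected related SAEs will be summarised". The grouping is by treatment received.
- **Adverse Events, Reporting Period**, on the period of collection: "Trial related AEs will be collected from time of randomisation (baseline visit) until the collection of the primary outcome".
- **Participant Withdrawal:** data collected before a participant withdraws or discontinues stay in the summaries and analyses.
- **Assessment of safety:** the summary follows treatment received. Events in people who did not receive their allocation are to be marked, not dropped.

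On timing, the Intervention group section says "It is our expectation that Cochlear implantation surgery occurs within 3 months following randomisation" and then "Following the implant surgery, a date for initial implant activation will be arranged, which defines first treatment activation for participants in the intervention arm". In Appendix 1 the first column after baseline is T0, and the adverse-effects row also starts there. The Appendix 1 footnote reads "T0 for CI arm – Either the date of CI activation or the date a decision was made that surgery would not take place".

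**The concern.** Membership of the safety population depends on having been assessed, not on having been randomised or treated. In the CI arm the operation, and the early recovery from it, come before the first scheduled assessment. A participant whose involvement ends in that gap can have an adverse event in the database and still be outside the set from which the safety tables are built.

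Safety of cochlear implantation is a named secondary objective. The protocol describes the surgery as irreversible, and the participants fall outside current NICE candidacy. In a trial of this size a few missing cases would visibly change the CI complication figures, always by removing surgical events. The hearing aid (HA) arm has no operation in the same interval, so no comparable events can be lost there.

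**Working it through.** **1. The denominator.** Inputs from Sample size and justification: difference 15, SD 24, two-sided 5%, power 90%, 15% non-collection.

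- Normal approximation: n = 2 × (1.960 + 1.282)² × 24² / 15² = 53.8, so 54 per arm. The two-sample t-test gives 54.8, so 55.
- Inflation: 55 / 0.85 = 64.7, so 65 per arm and 130 in total.

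The stated figures reproduce. I take 65 as the number operated in the CI arm, assuming that everyone allocated to CI has surgery.

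**2. The order of events in the CI arm.** Baseline assessments, randomisation, surgery (expected within 3 months), activation (T0), 1-month questionnaires, then clinic visits at 3, 6 and 9 months. Appendix 1 lists nothing between baseline and T0. Adverse events count from randomisation. The period in which events count therefore opens before the first scheduled assessment that would admit a participant to the set, and surgery lies in that gap.

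**3. Effect on the safety figures.** Let k be the number who have an event after surgery and are never assessed, and e the number with an event among the remaining CI participants. The rule as written gives e/(65 − k). Counting everyone operated gives (e + k)/65. The protocol gives no complication rate, so both k and e are assumed.

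| e | k | Rule as written | Everyone operated |
|---|---|---|---|
| 2 | 1 | 2/64 = 3.1% | 3/65 = 4.6% |
| 2 | 2 | 2/63 = 3.2% | 4/65 = 6.2% |
| 2 | 3 | 2/62 = 3.2% | 5/65 = 7.7% |
| 5 | 1 | 5/64 = 7.8% | 6/65 = 9.2% |
| 5 | 2 | 5/63 = 7.9% | 7/65 = 10.8% |
| 5 | 3 | 5/62 = 8.1% | 8/65 = 12.3% |

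Each case costs about 1/65 = 1.5 percentage points. The extreme is e = 0. One lost case then turns 1/65 (1.5%, exact 95% limits 0.04% to 8.3%) into 0/64 (upper limit 5.6%).

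**4. Chance that it happens at all.** If each operated participant has probability p of being such a case, the chance of at least one among 65 is 1 − (1 − p)^65. Assumed values of p from 0.5% to 3% give 28% to 86%. These only show how the answer depends on p.

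**5. Effect on the primary analysis.** Statistics, Methods says to "analyse as randomised without imputation of missing data". Anyone with no post-baseline assessment has no 9-month phoneme score and is already absent from that model. The rule removes 0 further participants and moves nobody between arms.

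**6. The T0 footnote.** For the CI arm it covers activation and a decision that surgery will not take place. It has no entry for someone operated on and never activated. Follow-up visits are timed from first activation, so this participant has no date to anchor them. The HA-arm definition, by contrast, ends in a fallback at 4 months after randomisation.

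**The case against.** The best defence is that the protocol's other sections already protect these events. Safety is summarised from randomisation, data from withdrawn participants are kept, and spontaneously reported events are recorded. Expected surgical complications go onto the eCRF and are reviewed by the trial management group and the data monitoring committee. Because a post-baseline assessment is undefined, the team could treat an adverse-event record or a post-operative scan as one. This stands in part: ongoing monitoring would see the events, and the problem is confined to the final tables. But the only sentence that defines the safety population sets a condition that those sections do not, Appendix 1 lists no such assessment before T0, and nothing says that an event record qualifies.

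A reader might also infer more than the text supports:

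- **That the rule breaks the as-randomised analysis.** It does not, as step 5 of the working shows.
- **That anyone with a serious peri-operative event is dropped.** A complication does not end follow-up. Under Participant Withdrawal, follow-up continues unless the participant leaves all aspects of the trial, and a single later assessment, even the 1-month home questionnaire, keeps them in the set.
- **That the exclusion acts on one arm only.** HA participants can also be lost before their fitting, which may be up to 4 months after randomisation. Only the loss of surgical events is one-sided.
- **That multiple imputation will omit early drop-outs.** The protocol does not name the population for imputation and leaves the methods to the SAP, which is not at hand. A clarifying sentence is sensible, but this is not an error.

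**Conclusion.** The safety definition is wrong as written. It conflicts with Safety outcomes, Participant Withdrawal and Assessment of safety, and any error it causes through lost surgical events understates the harm of implantation. The participants exposed are few: those who die or leave completely after surgery and before any assessment. The size is about 1.5 percentage points per case with 65 operated, or just over 4 points for three cases in the table above (for example 8.1% against 12.3%). The number of cases and the number of other events are assumptions. The primary efficacy comparison and the sample size of 130 are unaffected.

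**What to change.** 1. Define a separate safety set: all randomised participants, grouped by treatment received, classed as CI once surgery has started, with every event from randomisation counted and no assessment required.
2. State that any multiple-imputation sensitivity analysis includes all randomised participants, and define a post-baseline assessment if the term is kept for any other set.
3. Reconcile the CI-arm T0 definition in Appendix 1 with the visit schedule, so that a participant operated on but never activated is covered.

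This takes a few sentences in the protocol, carried into the SAP before database lock. It needs no new data collection and no change to the number randomised.
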